The plan is to enroll from 20 to 40 children and adolescent subjects with newly-diagnosed T1DM. Twenty will be randomized to the FIXED group and twenty will be randomized to the ICR group. The subjects will be selected from children and adolescents admitted to CHOA-Egleston with a diagnosis of new-onset Diabetes Mellitus. Participation in this study will be determined by a set of inclusion/exclusion criteria.

1) Inclusion Criteria

For enrollment in the study, subjects must: (1) Have Confirmed diagnosis of T1DM based on the most recent ADA criteria [16]; (2) Be 8 - 14 years of age; (3) Begin monitoring with a glucose monitor prior to discharge from the hospital; and (4) Have the ability to understand and be willing to adhere to the study protocol. (5) English or Spanish speakers.

2) Exclusion criteria

For enrollment in the study, subjects may not: (1) Have a clinically significant major organ system disease (i.e., hypertension, hyperlipidemia, or obesity); (2) Be on glucocorticoid therapy; (3) Have Type 2 Diabetes Mellitus; (4) Have Polycystic Ovarian Syndrome (PCOS); (5) Have a BMI > 85th %ile; (6) Have Acanthosis Nigricans; (7) Have any form of renal impairment; (8) Have Cystic Fibrosis; (9) Have Glucocorticoid-, Chemotherapeutic-, or any other Medication-induced form of Diabetes; (10) Be using any basal insulin other than Glargine insulin; (11) Have cognitive impairment (> 2 grades behind age-appropriate grade in school); (12) Be in Foster Care; (13) Have any history of DFCS involvement; and (14) If female, be pregnant or breast-feeding.

C. DATA MANAGEMENT

All data, including patient demographics, history, and laboratory tests will be collected on standardized forms and entered into an electronic database, REDCap. REDCap is a HIPPA-compliant, web-based, data capturing tool used in over 130 countries. Features include user-specific credentials, data-logging, longitudinal data modeling and more. Enrolled patients will be assigned a study ID. Subjects will only be identified in REDCap by their study ID. The patient's name, MRN and study ID will be kept in a secure file in a double lock in a filing cabinet under [name] supervision in the Emory Children's Center. Records will be maintained for 10 years as required for IRB studies.

D. OUTCOME MEASURES

1) Primary Outcome Measures

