The primary goal of this study is to determine the feasibility of a subsequent clinical trial of rapid acting insulin dosing for fixed carbohydrates (FIXED group) vs ICR with variable carbohydrate intake (ICR group). In doing so, we will examine our ability to recruit and consent patients (>70% consent rate), study retention (>90% retention), completion of study visits (average session attendance \geq 90%), study measures (\geq 90% measure completion), caregiver treatment adherence, and post-treatment satisfaction (\geq 90%),

2) Secondary Outcomes Measures

Secondary outcome measures will include caregiver anxiety and glycemic variability. Each of these measures are described below.

One secondary outcome measure is caregiver anxiety. This will be assessed by a parental stress scale [17]. The caregiver will fill out the questionnaire at initial enrollment (prior to hospital discharge) and at each clinic follow-up throughout the study. We will use the Spanish adaptation of parental stress scale (PSS) [18] for Spanish population if necessary.

We clarify in the survey that the questions are to be answered in terms of how the caregiver-child relationship exists since the diagnosis of diabetes mellitus.

The scales are shown in **Annex 1 and 2**

Glycemic variability (GV) is another secondary outcome measure. The GV will be calculated in all subjects through the use of a glucose monitor (GM) data classification scale. Subjects will be considered to have appropriate GV if their blood glucose level is in the range of 80 mg/dL – 180 mg/dL (Group C).

The GV classification is as follows:

Group A: < 50 mg/dl.

Group B: 50 – 79 mg/dl

Group C: 80 – 180 mg/dl

Group D: 181 – 350 mg/dl

Group E: > 350 mg/dl

Safety is the last secondary outcome measure. The safety measured that will be compared in both groups include death, risk of life threatening event (i.e., severe hypoglycemia associated with seizure or altered mental status), hospitalization for diabetes complication (diabetic ketoacidosis or hypoglycemia), and risk of disability or permanent damage.

E. STATISTICAL CONSIDERATIONS

Randomization

Randomization will be performed by study statistician using random-permuted blocks of size 2 and 4. Randomization assignments will be placed in sealed, opaque envelopes to be stored. Study investigators will not be blinded to treatment assignment.

Sample Size

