A goal of 20 patients is necessary for this study, but we will reach up to 40 participants in case there is any withdraw after consented and randomized. While the overall goal of the study is to demonstrate feasibility of a subsequent randomized controlled trial, limited efficacy testing will be performed. Given a sample size of 20 participants (10/grp), we will have greater than 90% power to detect a minimum standardized mean difference of 1.25 (i.e., approximately a 1.25 standard deviation difference) between groups. Effect sizes will be calculated for all study measures of interest and be used in future power calculations. On average, there are ~25 new type I/II diabetics diagnosed at Egleston hospital each month. Assuming an eligibility rate of 40%, 10 patients would be eligible to participate each month. Based on this, we are confident in our capacity to recruit 20 to 40 participants during the study period with the goal of having 20 participants to complete the study.

Statistical Analysis

Demographic characteristics will be summarized for both groups using means and standard deviations, medians and quartiles, or counts and percentages, as appropriate based on distribution. T-tests, Wilcoxon rank sums, and/or Chi squared tests will be used to assess differences between the two groups.

Primary Aims: Measures of feasibility (consent, retention, engagement, satisfaction, etc.), will be summarized overall and by group, when applicable.

Secondary Aim 1: Parental stress scale

The parental stress scale will be scored per the instrument's instructions. The total scores for the treatment groups will be compared in a cross-sectional fashion using t-tests or Wilcoxon rank sums tests as appropriate based on the distribution of scores. Changes in parental distress over-time will be evaluated using two-way repeated measures analysis of variance models. Models will include the main effect of treatment assignment, time (baseline, 1 month, 4 months), and the treatment X time interaction. The interaction term will serve as the primary statistical test for aim 2. Summary statistics, statistical significance, and effect sizes will be reported by group at each time point of interest, when applicable.

Secondary Aim 2: Glycemic variability

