Glycemic variability will be examined both as a continuous variable and a categorical variable using the ranges defined in section D. Time series analysis will be used to examine daily measures of blood glucose (obtained from patient diary's) during the study period. Variability will be measured as the probability of acute change (PAC), using methods described by Jahnig et al. (2008). Acute changes will be adjusted for time between readings. In addition, first-order autocorrelations and/or mean-square successive difference will be used to examine variation in readings as described by Jahnig. Multilevel modeling will be used to test between-group differences in variability.

Secondary Aim 3: Safety

Adverse event of interest and serious adverse events (see section D) will be summarized overall and by treatment group. For participants experiencing more than 1 episode of a specific event (e.g., severe hypoglycemia), the maximum grade and severity will be recorded. Chi-square tests will be used to compare the frequency of events between the two cohorts.

Given the exploratory nature of these secondary outcomes, we will calculate effect sizes based on the adjusted means and standard deviations or differences in proportions, when appropriate.

All analyses will be conducted using SAS v9.4 (Cary, NC).

F. ANTICIPATED RESULTS

This research will be feasible to develop a successful larger clinical trial. Due to the fixed regimen seeming to be less complicated, because there are less calculations to make than in those using the ICR group, we anticipate that parental anxiety will be decreased in the FIXED group. This will encourage more blood glucose monitoring and treatment compliance. Therefore, we anticipate GV to be decreased for the FIXED group.

G. LIMITATIONS

The major limitations of this study are related to caregiver's self-completion questionnaire and ability to contact study personnel frequently during the study period in order to report blood glucose levels and implement the insulin adjustments. More than likely, multiple insulin regimens should work, but the idea behind this study is that the fixed regimen may be easier to implement.

[figure not shown]

Figure 2: Proposed protocol.

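### Safety events with 10 to 20 participants per arm are to be compared by chi-square: the approximation is unsupported, a null result says little, and episode counts by arm are not planned (minor)

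*Combined protocol and SAP*

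**What the plan says.** Section 5.E, Secondary Aim 3, says of adverse events that "Chi-square tests will be used to compare the frequency of events between the two cohorts". It does not say whether a continuity correction applies, and it names no exact test or rule for small cells. For a participant with several episodes of one event type, "the maximum grade and severity will be recorded".

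Section 5.D lists what is compared: death, life-threatening events such as severe hypoglycemia with seizure or altered mental status, "hospitalization for diabetes complication (diabetic ketoacidosis or hypoglycemia"), and lasting harm or disability. No event rates are given.

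On arm size, Section 5.E states that "A goal of 20 patients is necessary for this study, but we will reach up to 40 participants". Section 5.B gives the upper end: "Twenty will be randomized to the FIXED group and twenty will be randomized to the ICR group". Randomization uses "random-permuted blocks of size 2 and 4", so arms should be close to equal before withdrawals.

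Three other statements bear on the point. Section 5.E summarizes events by group, calls the secondary outcomes exploratory, and provides for effect sizes or differences in proportions where suitable. Section 12 has diabetes-related adverse events documented, counted and reported to the IRB. For its quantitative outcomes, Section 5.E allows a t-test or a Wilcoxon test depending on the distribution; the safety comparison has no such alternative.

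**The concern.** The chi-square p-value is a large-sample approximation. Serious events in arms of 10 to 20 are where it is least secure, and here it is the only test named. The reported p-value for a sparse table could then depend on the approximation as much as on the data.

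The more practical danger runs the other way. With so few participants, almost any safety comparison will be non-significant, and a reader may take that as reassurance that the two mealtime regimens are equally safe.

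Secondly, hypoglycemia can recur, and its frequency could differ between regimens. A between-arm comparison with one entry per participant cannot show a difference that lies in repeat episodes.

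**Working it through.** **Plan's own figure.** The plan gives no power or type I error for safety. Its one power statement ("Given a sample size of 20 participants (10/grp), we will have greater than 90% power to detect a minimum standardized mean difference of 1.25") concerns a difference in means. A two-sided 5% t-test with those inputs gives 75.3%, so the figure is not reproduced, but that is a separate matter and does not bear on this point.

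**Inputs.** Arms of 10 or 20 (Sections 5.B and 5.E). Assumed, because the plan is silent: two-sided 5% level, uncorrected Pearson chi-square, and true event rates per participant of 5% to 20%.

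**1. Expected counts.** With equal arms and m participants affected in total, each event cell has expected count m/2, which is below 5 unless m is at least 10.
- 10 per arm: P(m ≤ 9) for Binomial(20, 0.20) is 99.7%, and higher at lower rates.
- 20 per arm: P(m ≤ 9) for Binomial(40, p) is 99.5% at p = 10% and 73% at p = 20%.

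**2. Single tables.** Chi-square = N(ad − bc)² / (product of the four margins).
- 0/10 v 4/10: 20 × 40² / (10 × 10 × 4 × 16) = 32000/6400 = 5.00, p = 0.025. Fisher: 2 × C(10,4)/C(20,4) = 2 × 210/4845 = 0.087.
- 0/20 v 4/20: 40 × 80² / (20 × 20 × 4 × 36) = 256000/57600 = 4.44, p = 0.035. Fisher: 2 × 4845/91390 = 0.106.

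| Table | Chi-square | Fisher | Boschloo |
|---|---|---|---|
| 0/10 v 4/10 | 0.025 | 0.087 | 0.042 |
| 1/10 v 6/10 | 0.019 | 0.057 | 0.023 |
| 0/20 v 4/20 | 0.035 | 0.106 | 0.061 |

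**3. Overall type I error.** For a common event rate p, sum the two binomial probabilities over every table with p-value ≤ 0.05.

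| Arms | 5% rate | 10% rate | 20% rate | Maximum (at rate) |
|---|---|---|---|---|
| 10 v 10 | 0.1% | 0.9% | 3.0% | 4.2% (50%) |
| 9 v 11 | 0.6% | 2.4% | 5.3% | 5.7% (27%) |
| 8 v 12 | 0.3% | 1.5% | 4.2% | 5.9% (36%) |
| 20 v 20 | 1.2% | 3.9% | 5.0% | 5.3% (31.5%) |

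An 11 v 10 split peaks slightly higher, at 6.4% (32%). No split in this check exceeds 5% at rates of 10% or less. Fisher at 10 v 10 has a maximum of 1.3%.

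**4. What a null result means.** For true rates of 5% v 20%, power at 10 per arm is 7.5% (chi-square) or 2.0% (Fisher); at 20 per arm it is 29.2% or 16.8%. With zero events in n, the upper two-sided 95% limit is 1 − 0.025^(1/n): 31% for n = 10 and 17% for n = 20.

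**5. Repeat episodes (invented counts, for illustration).** Suppose 3/10 children are affected in each arm, with 12 episodes in one arm and 3 in the other. By participant, p = 1.00. Splitting 15 episodes 12 to 3 gives 2 × (455 + 105 + 15 + 1)/2¹⁵ = 1152/32768 = 0.035. That treats episodes as independent, which episodes within one child are not, so it shows only that the information is hidden, not how strong it would be.

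**The case against.** The strongest reply is that the chi-square test is not anti-conservative in this trial as planned. At 10 v 10 it rejects too rarely, not too often, and the Boschloo test also falls below 0.05 for 0 v 4, 1 v 6 and 2 v 7. Moving to Fisher would cut power that is already very low. All of this stands.

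A reader might infer from the single tables that chi-square p-values are generally too small. The enumeration does not support that. It is true that, given exactly 4 affected participants, the false-positive rate is 8.7% (10 per arm) or 10.6% (20 per arm). Given 1, 2 or 3 it is zero, and given 5, 6 or 8 at 10 per arm it is 3.3%, 1.1% and 2.0%. Nor is chi-square below every exact p-value: for 0/20 v 5/20 it is 0.0168 and Barnard's exact test gives 0.0167. A continuity-corrected chi-square, which the plan does not rule out, gives 0.094 for 0/10 v 4/10, close to Fisher.

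On recurrence, one row per participant is a standard convention that keeps observations independent. The plan does not say that episodes are discarded; Section 12 has events counted, and low glucose readings enter the Secondary Aim 2 analysis. What remains is narrower: no episode count or rate is planned by arm.

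A reader might also infer that a regimen would be declared less safe on this p-value. The plan contains no such decision rule.

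**Conclusion.** The point holds in a limited form. The condition that supports the chi-square approximation will almost certainly fail at 10 per arm, and will probably fail at 20 per arm for event rates up to 20%. Individual p-values can then differ materially from exact ones, in places across 0.05. Overall false positives are not inflated at 10 v 10. Excesses above 5% are modest, need larger or uneven arms, and peak at event rates near 27% to 36%, which are not rare. The greater weakness is that a non-significant result carries almost no information about equal safety, and the plan does not say so. The missing episode summary by arm is a separate, small gap.

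These conclusions rest on the assumed event rates, a two-sided 5% level and the uncorrected form of the test. Severity is minor: the analysis is secondary and exploratory, in a pilot whose primary goal is feasibility.

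**What to change.** In Section 5.E, Secondary Aim 3:

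- Make the main safety output the number of participants with at least one event, by arm, with the risk difference and an exact 95% CI. The plan already provides for differences in proportions, so only the exact interval is new.
- If a p-value is given, replace chi-square with an exact test. An unconditional test such as Boschloo's is preferable, given Fisher's maximum size of 1.3% and its power of 2.0% in the example above. The statistician should confirm that the chosen test can be run in SAS 9.4.
- Beside the worst grade, report total episodes and episodes per participant-month by arm, using each participant's actual follow-up.
- State that absence of statistical significance is not evidence of equal safety.

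The cost is a few sentences and slightly more analysis work. No new assessments should be needed if each episode counted under Section 12 is kept with its date. If Fisher's test is chosen, some power is lost.

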6. DATA COLLECTION FOR FUTURE RESEARCH

Records will be maintained for 10 years as required IRB studies.

7. COMMUNITY PARTICIPATION

Not applicable

8. PARTICIPATION SELECTION

Study subjects will be selected from the cohort of pediatric patients with newly diagnosed of type 1 diabetes mellitus hospitalized at Children’s Health of Atlanta and followed at diabetes clinic in the Center for Advanced Pediatrics Georgia. Parents will consent and subjects will assent for the subject to enroll in the research study.

9. INFORMED CONSENT

During hospitalization for newly diagnosed of type 1 diabetes mellitus. The study will be initially discussed, parents and participants will be provided with a HIPAA compliance form and consent/assent form.

10. INCIDENTAL FINDINGS

Not applicable

11. COMPENSATION FOR TIME & EFFORT

No monetary compensation will be provided to participants. Participants will not be charged for any of the research activities.

12. DATA & SAFETY MONITORING PLAN (DSMP)

There will not be an independently constituted data safety and monitoring board for this protocol because it does not involve an experimental intervention. Instead, this study will have a data safety and monitoring plan (DSMP). This plan includes examination of consent rates, attrition, and safety related data. The plan will be generated by the study statistician in conjunction with the PIs of the study. Presentation of data will be presented in a blinded fashion with treatments de-identified. The first DSMP will be reviewed after 12 patients enroll in the study, then subsequently every 6 months of the study. There are no plans for an interim analysis as this is a pilot study.

All relevant adverse events related with diabetes will be documented and reviewed by the principal investigator. These will be enumerated and reported according to IRB policies. Any serious adverse events will be reported within 24 hours to the IRB. They will be reviewed by all investigators and a disposition determined before proceeding with further enrollment. There are no additional laboratory evaluations outside of the routine care for patients with diabetes mellitus.

The procedures associated with this research trial are associated with minimal risk.

13. POTENTIAL BENEFITS

Participation in this study offers appropriate plans that are well-established and have been utilized to help children and adolescents with T1DM maintain appropriate glycemic control. Although the research may not benefit the subject initially and directly, the results of the study could lead to develop bigger clinical trial to demonstrate alterations of current management options for children and adolescents with newly-diagnosed T1DM.

14. ADVERSE EVENTS & RISKS

There are minimal risks associated with GM. A GM is a self-monitoring of blood sugars via finger-stick that help making treatment decisions about diabetes. There is a small possibility that the measurements may not be accurate. We will consider these factors that affect meter accuracy and the steps to resolve or prevent the problems like test strip problems (Be sure the strips are meant for the meter), keeping the glucose meter and test strips at extreme temperatures (Keep glucose meter at room temperature), improper test strip coding, problems inserting the test strip in the monitor or not enough blood applied to test strip (recommend a generous drop of blood to test strip).

Regarding capillary sampling by finger-stick with a lancet, can carry a small risk of the following: infection, bleeding, pain or local skin irritations including redness, swelling, bruising, itching, scarring or skin discoloration.

15. CONFIDENTIALITY

The study will comply with HIPAA guidelines regarding confidentiality of participant data. Privacy will be assured during the consent and study procedures. During the consent process, potential subjects and their parents will be allowed time to review the informed consent document and ask a member of the research team all their questions regarding the research study. All questionnaires will be labeled with a

study ID. Data, including paper copies of participant data, original signed consent and HIPAA documents, completed questionnaires, and all source documents, will be stored in a medical building with card-coded access inside a locked cabinet. Data stored on the computer will be encrypted and password protected. A separate file will be kept on an encrypted and password protected computer that will contain participant identifiers linking names and contact information to the study for purpose of follow up in this clinical trial. This information will not be entered into the computer system for study data. At completion of study, all participants' identifiable information will be stored at Access Data Management System for a period of 10 years. After 10 years, all information will be destroyed. When papers are published regarding this study and data obtained, only composite data will be used, and each subject's identity will be strictly protected.

Although IRB policies to protect confidentiality of study information will be followed, it is possible that a breach could occur. The following steps will be taken to limit that possibility: 1) Source documents for the study will be stored either in the CHOA HER (Epic) or as hard copies in locked filing cabinets in a locked office at Center for Advanced Pediatrics, 2) All subjects will be assigned a study number and all study records will bear only that number for identification. The key for identifying individual subjects will only be available to study personnel.

14. Sunghwan Suh, Jae Hyeon Kim. Glycemic Variability: How Do We Measure It and Why Is It Important?. *Diabetes Metab J.* 2015; 39(4): 273-282.
15. Shapiro, Jenna B; Vesco, Anthony T ; Weil, Lindsey E G ; Evans, Meredyth A ; Hood, Korey K ; Weissberg-Benchell, Jill. Psychometric Properties of the problem Areas in Diabetes: Teen and Parent of Teen Versions. *Journal of pediatric psychology*, 01 2018, Vol.43(5),pp.561-571
16. American Diabetes Association. 2. Classification and diagnosis of diabetes: Standards of Medical Care in Diabetes—2019. *Diabetes Care* 2019;42(Suppl. 1):S13–S28
17. Berry, JD, & Jones, W,H. The Parental Stress Scale : initial psychometric evidence. *Journal of Social and Personal Relationships* 1995; 12 (3):p. 463-472. <https://doi.org/10.1177/0265407595123009>
18. Oronoz, Beatriz; Alonso-Arbiol, Itziar; et al. A Spanish Adaptation of the Parental Stress Scale *Psicothema.* 2007; 19 (4): 687 -692. ISSN: 0214-9915

Parental Stress Scale

The following statements describe feelings and perceptions about the experience of being a parent with a child with new onset type 1 diabetes mellitus. Think of each of the items in terms of how your relationship with your child typically is in the setting of recently diagnosis of diabetes mellitus. Please indicate the degree to which you agree or disagree with the following items by placing the appropriate number in the space provided.

1 = Strongly disagree 2 = Disagree 3 = Undecided 4 = Agree 5 = Strongly agree

1	I am happy in my role as a parent	
2	There is little or nothing I wouldn't do for my child(ren) if it was necessary.	
3	Caring for my child(ren) sometimes takes more time and energy than I have to give.	
4	I sometimes worry whether I am doing enough for my child(ren).	
5	I feel close to my child(ren).	
6	I enjoy spending time with my child(ren).	
7	My child(ren) is an important source of affection for me.	
8	Having child(ren) gives me a more certain and optimistic view for the future.	
9	The major source of stress in my life is my child(ren).	
10	Having child(ren) leaves little time and flexibility in my life.	
11	Having child(ren) has been a financial burden.	
12	. It is difficult to balance different responsibilities because of my child(ren).	
13	The behavior of my child(ren) is often embarrassing or stressful to me.	
14	If I had it to do over again, I might decide not to have child(ren).	
15	I feel overwhelmed by the responsibility of being a parent.	
16	Having child(ren) has meant having too few choices and too little control over my life.	
17	I am satisfied as a parent	
18	I find my child(ren) enjoyable	

Scoring:

To compute the parental stress score, items 1, 2, 5, 6, 7, 8, 17, and 18 should be reverse scored as follows: (1=5) (2=4) (3=3) (4=2) (5=1). The item scores are then summed.

Scoring the tool:

We want a low score to signify a low level of stress, and a high score to signify a high level of stress

- Overall possible scores on the scale range from 18 – 90.
- The higher the score , the higher the measured level of Parental stress

Use a simple table to show the before and after results to evidence whether an intervention has had a positive effect.

- Comparison of individuals before / after or longitudinal overall Parental Stress Scale scores.
- The comparison of before and after mean average scores for groups (parents/care givers accessing the particular intervention/group sessions, service or provision).

Escala de Estres Parental

Las siguientes oraciones describen sentimientos y percepciones acerca de como un padre/madre/cuidador se siente cuidando a un niño que ha sido diagnosticado con diabetes mellitus recientemente. Responder cada pregunta pensando en como es la relacion entre su niño(a) con usted desde el diagnostico de diabetes mellitus.

Indicar el grado de acuerdo o desacuerdo en cada una de las siguientes preguntas y coloque el numero apropiado en el espacio correspondiente.

- 1 = Totalmente en desacuerdo
- 2 = Desacuerdo
- 3 = Indeciso
- 4 = De acuerdo
- 5 = Totalmente de acuerdo

1	Me siento feliz en mi papel como padre/madre	
2	No hay nada o casi nada que no haria por mi hijo/a si fuera necesario	
3	Atender a mi hijo/a a veces me quita mas tiempo y energia de la que tengo.	
4	A veces me preocupa el hecho de si estoy hacienda lo suficiente por mi hijo/a	
5	Me siento muy cercano/a a mi hijo/a	
6	Disfruto pasando tiempo con mi hijo/a	
7	Mi hijo/a es una fuente importante de afecto para mi	
8	Tener un hijo/a me da una vision mas certera y optimista para el future	
9	La mayor fuente de estres en mi vida es mi hijo/a	
10	Tener un hijo/a deja poco tiempo y flexibilidad en mi vida.	
11	Tener un hijo/a ha supuesto una carga financiera	
12	Me resulta dificil equilibrar diferentes responsabilidades debido a mi hijo/a	
13	El comportamiento de mi hijo/a menudo me resulta incomodo o estresante	
14	Si tuviera que hacerlo de Nuevo, podria decidir no tener un hijo/a	
15	Me siento abrumado/a por la responsabilidad de ser padre/madre	
16	Me siento satisfecho/a como padre/madre	
17	Disfruto de mi hijo/a	

Scoring:

Participants will be asked to rate each one on a 1-to-5 Likert-type response scale ranging from 1 (strongly disagree [*totalmente en desacuerdo*]) to 5 (strongly agree [*totalmente de acuerdo*]). The items appeared in the same order as in the English-language PSS (except for the eliminated item 16 in the English version.). The total score was obtained by summing up the value for each item (reversed items are 1, 2, 5, 6, 7, 8, 16, and 17). A higher score indicates a higher level of parental stress.

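### Parental Stress Scale totals from the 18-item English form and the 17-item Spanish form would be pooled as one score, adding small but avoidable noise to the arm comparisons and effect sizes

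*Combined protocol and SAP*

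**What the plan says.** Section 5.B makes English and Spanish speakers eligible. Section 5.D provides the Spanish adaptation of the scale where it is needed. The two forms are printed after the reference list (Annexes 1 and 2).

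- **English form, Scoring.** "To compute the parental stress score, items 1, 2, 5, 6, 7, 8, 17, and 18 should be reverse scored", and then "The item scores are then summed". The form lists 18 items. The note on scoring the tool gives the lower limit: "Overall possible scores on the scale range from 18"; the upper limit is 90.
- **Spanish form, Scoring.** The form lists 17 items: "The items appeared in the same order as in the English-language PSS (except for the eliminated item 16 in the English version". Scoring is again a plain sum: "The total score was obtained by summing up the value for each item". No range is printed.
- **Section 5.E, Secondary Aim 1.** "The parental stress scale will be scored per the instrument's instructions". Then: "The total scores for the treatment groups will be compared in a cross-sectional fashion using t-tests or Wilcoxon rank sums tests". Also: "Summary statistics, statistical significance, and effect sizes will be reported by group at each time point of interest". The repeated-measures model contains treatment, time and their interaction, and the interaction is named as the main test for aim 2.
- **Section 5.E, Randomization.** Permuted blocks of 2 and 4; no stratification by language is described.
- **Section 5.E, Sample Size.** Effect sizes from this pilot are to be used in later power calculations.

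**The concern.** The scoring sentence in Secondary Aim 1 points to one set of instructions, but the annexes hold two, and they produce totals with different item counts. An analyst who follows the text exactly would put an 18-item sum and a 17-item sum into the same t-test or Wilcoxon test. Nothing in the plan rescales either form, restricts both to their shared items, or adjusts for form.

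The outputs at stake are the cross-sectional comparisons, the group means at each visit, and the effect sizes handed on to the later trial. A group mean that mixes the two sums has no single defined range. If no rule is set in advance, the choice among raw, shared-item and prorated scores would fall to a team that is not blinded to treatment, possibly after the data have been seen.

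**Working it through.** **1. Ranges.** Each item scores 1-5.
- English: 18 × 1 = 18 to 18 × 5 = 90. This reproduces the printed range.
- Spanish: 17 × 1 = 17 to 17 × 5 = 85 (derived).

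**2. How the forms differ.** English items reversed: 1, 2, 5, 6, 7, 8, 17, 18. Spanish items reversed: 1, 2, 5, 6, 7, 8, 16, 17. Once English item 16 is removed, English 17 and 18 become Spanish 16 and 17, so the lists match one to one. The scoring difference is therefore English item 16 alone. It is not reversed and adds 1-5 points. A caregiver scoring 3 on every item after reversal gets 18 × 3 = 54 in English and 17 × 3 = 51 in Spanish.

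**3. Assumptions.** The documents give no Spanish share *p*, no mean *m* for item 16 and no SD for the total. I take *p* = 10-50%, *m* = 3 (range 2-4, hard limits 1-5) and SD = 6-12. The arm size *n* is 10 (Sample Size) or 20 (section 5.B).

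**4. Shift for a given imbalance.** Shift = (difference in Spanish counts / *n*) × *m*.
- *n* = 10, imbalance of 2: 2/10 × 3 = 0.6 points (0.4-0.8 for *m* = 2-4; limits 0.2-1.0).
- *n* = 20, imbalance of 2: 2/20 × 3 = 0.3 points (limits 0.1-0.5).

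**5. Chance of an imbalance of 2 or more.** The two counts are treated as independent Binomial(*n*, *p*).

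| *p* | *n* = 10 | *n* = 20 |
|---|---|---|
| 10% | 24% | 42% |
| 20% | 39% | 55% |
| 30% | 46% | 60% |
| 50% | 50% | 64% |

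**6. Against sampling error, *n* = 10.** SE of the mean difference = SD × √(2/10): 6 × 0.447 = 2.7 and 12 × 0.447 = 5.4. A 0.6-point shift is 0.6/2.68 = 22% or 0.6/5.37 = 11% of that SE, and 0.10 or 0.05 SD. This describes one given imbalance, not the average cost.

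**7. Average cost, *n* = 10.** SD of the chance shift = *m*√(2*p*(1−*p*)/*n*). At *p* = 30%: 3 × √(2 × 0.3 × 0.7/10) = 0.61. If item 16 varies with an assumed SD of 1: √(2 × [0.3 × 10 − 9 × 0.09]/10) = 0.66. Independent errors add in quadrature. With item 16 fixed at 3:
- *p* = 30%, SD 6: √(7.2 + 0.378)/√7.2 = 1.026, so 2.6% more.
- *p* = 30%, SD 12: √(28.8 + 0.378)/√28.8 = 1.0065, so 0.65% more.
- *p* = 10%: 1.1% (SD 6) and 0.3% (SD 12).

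A standardized difference of 1.25 would become 1.22 (1.25/1.026) or 1.24 (1.25/1.0065) at *p* = 30%.

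**8. Bias.** The expected difference in counts is zero, so the expected shift is zero. In an item-level simulation with 10 per arm, type I error for the mixed sum was 0.047-0.048 at Spanish shares of 20% and 40%.

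**9. Interaction.** If each caregiver keeps the same form, the offset largely cancels in the change score. A uniform change of 0.5 per item is 18 × 0.5 = 9.0 points in English and 17 × 0.5 = 8.5 in Spanish. An imbalance of 2 in 10 then moves the difference in change by 2/10 × 0.5 = 0.1 points.

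**The case against.** The strongest reply is that this hardly matters. There is no bias, the feasibility primary is untouched, the secondary outcomes are declared exploratory, and the one test named as primary for aim 2 moves by about 0.1 points. Quoting 11-22% of the standard error overstates the effect; the average inflation of 0.3-2.6% is the fairer measure. A change of 0.01-0.03 in an effect size estimated from 10 per arm would not alter a later power calculation. All of that stands, and it limits how much weight the point can bear.

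Three narrower objections also stand. Mixing needs at least one caregiver on each form. The language criterion is written for subjects, whereas the caregiver completes the scale, so it supports Spanish-form use only indirectly. Every input to the size is assumed, and the number of Spanish forms may be zero.

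On the remedy, using 17 items drops one collected item for English-form caregivers and makes the analysed score depend on who enrols. An item mean (1-5 on both forms) or an 18/17 prorated Spanish sum (17 × 18/17 = 18 to 85 × 18/17 = 90) would also align the ranges and keep all English items. In the simulation at a 40% Spanish share the average effect size was 1.150 for the mixed sum, 1.156 for the 17 shared items and 1.160 for the item mean, so the choice among remedies matters little.

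None of this rescues the scoring rule as written, which still pools totals that are not comparable.

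**Conclusion.** The concern holds. When both forms are used, the plan as written analyses an 18-item sum and a 17-item sum as one variable, with a built-in offset of 1-5 points per Spanish form. That mismatch follows directly from the two scoring notes.

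The consequence is modest chance error in the cross-sectional tests, visit means and effect sizes. With 10 per arm it is 0.6 points for each imbalance of two forms, and about 0.3-2.6% on the standard error at Spanish shares of 10-30%. Both figures assume an item-16 mean of 3; the second also assumes an SD of 6-12. The rule should be corrected because it is wrong and cheap to put right, not because it threatens the trial's conclusions.

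**What to change.** In section 5.E, Secondary Aim 1, replace the sentence "The parental stress scale will be scored per the instrument's instructions" with:

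> Items will be reverse-scored per each form's instructions. If any caregiver uses the Spanish form, the analysed score for every caregiver is the sum of the 17 items common to both forms (English item 16 omitted; range 17-85), and the 18-item English total is reported descriptively; otherwise the 18-item total is analysed. The number of caregivers using each form is reported by arm.

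The cost is one sentence replaced by three. No new data are needed, since both forms already collect the 17 items. The downside is that, once a Spanish form is used, the analysed English score is no longer the full 18-item total. If the team prefers to keep every English item, a prespecified item mean or 18/17 prorated sum would also put the forms on one range. No option here shows that the two language versions measure stress equivalently; the change removes only the mechanical offset.
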